5.1.2. Part B

Part B of this study will include a total of 14 visits and will be approximately 5 weeks in duration as described below.

- Up to a 2-week screening period
- 2-week double-blind treatment period (Week 1 inpatient, Week 2 outpatient)
- 1-week outpatient safety follow-up period

Approximately 120 participants are planned for randomization in the double-blind treatment period (40 placebo participants, 40 AGN-241751 3 mg participants, 40 AGN-241751 25 mg participants). Eligible participants will be randomized in a ratio of 1:1:1 to one of 3 double-blind oral administration treatment groups: 3 mg dose of AGN-241751, 25 mg dose of AGN-241751, or placebo, administered BID. Participants who enrolled (were randomized) in Part A will not be permitted to screen into Part B (and vice versa).

Screening Period

After providing written consent, participants will enter a screening period of up to 14 days. Screening procedures may be conducted on up to 2 separate dates where necessary to accommodate participant and site schedule; however, every effort should be made to conduct all procedures as early as possible in the screening period. Participants will wash out of any ADT and prohibited medications under the supervision of the study investigator staff during the screening period. At Visit 2 (Day -1), study procedures required to determine eligibility will be completed prior to admission to the clinic. Participants meeting the eligibility criteria at Visit 2 (Day -1, Baseline) will be admitted to the inpatient facility, and the remainder of the Visit 2 study procedures will be completed. A urine pregnancy test should be done on Day -1 (at baseline), if more than a week has passed since the serum pregnancy test was done at Screening. Participants are required to not use any nicotine substances 1 hour prior to administration of the HVLT-R.

Double-Blind Treatment Period

Participants will be randomized in a ratio of 1:1:1 to 1 of 3 treatment groups (AGN-241751 3 mg BID, AGN-241751 25 mg BID, or placebo BID) for the 2-week double-blind treatment.

Participants will be administered 1 tablet in the morning and 1 tablet in the afternoon. At Visit 3 (Day 1), the participant will be randomized and assigned a treatment by the interactive web response system (IWRS), and the 1st dose of study medication will be administered in the morning after all predose assessments have been completed.

Week 1 Inpatient Double-Blind Treatment Period

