9.2.7. Medication Errors

Medication error refers to any unintended error in the dosing and/or administration of the study treatment as per instructions in the protocol. Medication errors generally fall into 4 categories as follows:

- Wrong study drug
- Wrong dose (including dosing regimen, strength, form, concentration, amount)
- Wrong route of administration
- Wrong participant (ie, not administered to the intended participant)

Medication errors include occurrences of overdose and underdose of the study treatment. For Part B, participants should be instructed as described in Section [7.2](#) (Dose Modification) for missed doses.

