9.5. Pharmacokinetics (Part B Only)

In Part B of this study, collection of a single CSF sample is an optional procedure, as participants may/may not choose to allow this sample collection without impacting their participation in the study. For those participants who agree and have given consent to provide a CSF sample for PK analysis, lumbar puncture will be used to collect CSF, and a maximum of 4 mL of CSF will be collected. Collection of CSF is preferred at Visit 5 (Day 3), but can be done at Visit 4 or Visit 6, either immediately prior to the morning dose or at 8 hours after the morning dose. Within each site, 1 sample per participant will be collected, and study staff will alternate between predose and postdose for participants (eg, 1st participant sample is collected predose, 2nd participant sample is collected postdose, 3rd participant sample is collected predose, etc.). Additional details of the CSF sample collection, handling, and storage are presented in [Appendix 18](#).

Additional exploratory analysis may be performed on collected CSF samples.

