10.2.2. Part B

The analysis populations in Part B will consist of participants as defined below:

- The mITT population includes all randomized participants who received at least 1 administration of study treatment and have a baseline MADRS total score and at least 1 postbaseline assessment for the MADRS total score during the double-blind treatment period. Participants will be summarized according to the randomized study treatment.
- The safety population includes all participants who received ≥ 1 administration of study treatment. Participants will be summarized according to the study treatment they actually received.
- The PD population includes all randomized participants who received ≥ 1 administration of study treatment and have Day -1 qEEG and ERP assessments and at least 1 postbaseline assessment for the qEEG and ERP assessments during the double-blind treatment period. Participants will be summarized according to the randomized study treatment.
- The PK population includes all randomized participants who received ≥ 1 administration of study treatment and have at least 1 CSF collection in Part B. Participants will be summarized according to the randomized study treatment.

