10.3.3. Pharmacokinetic Analysis (Part B Only)

Analysis of the CSF concentrations of AGN-241751 will be performed using the PK population for the double-blind treatment period. Descriptive analysis of the CSF concentrations will be performed.

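### Part B groups CSF concentrations by randomised arm, so if a participant took another arm's tablets before sampling, the value would be reported under a dose not taken

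*Protocol*

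**What the plan says.** Protocol Section 10.2.2 lists four Part B analysis populations, each with its own grouping rule. The PK population consists of randomised participants who had at least one administration of study treatment and "have at least 1 CSF collection in Part B. Participants will be summarized according to the randomized study treatment". In the same list, the rule for the safety population is different: "Participants will be summarized according to the study treatment they actually received".

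Section 10.3.3 gives the PK population its single use: "Analysis of the CSF concentrations of AGN-241751 will be performed using the PK population for the double-blind treatment period". It then limits the analysis: "Descriptive analysis of the CSF concentrations will be performed". No test or between-arm estimate is planned on these data.

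Section 9.5 makes CSF sampling optional. It is preferred on Day 3 and possible on Day 2 or Day 4, either just before the morning dose or 8 hours after it. Within a site, "1 sample per participant will be collected, and study staff will alternate between predose and postdose for participants". The planned arms in Section 5.1.2 are "40 placebo participants, 40 AGN-241751 3 mg participants, 40 AGN-241751 25 mg participants", all dosed twice daily.

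Section 9.2.7 names "Wrong study drug" and "Wrong dose (including dosing regimen, strength, form, concentration, amount" among the categories of medication error. Nothing in the supplied documents removes a misdosed participant from the PK population or moves that participant's sample to the dose taken. The supplied SAP covers Part A only and defines no PK population.

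**The concern.** Grouping by randomised arm protects a randomised comparison from bias introduced after randomisation. Section 10.3.3 plans no such comparison on CSF concentrations, so the rule gives no protection here. It also carries a risk, because a drug concentration is a direct consequence of what was ingested. Under the rule as written, a participant randomised to 3 mg who was given 25 mg tablets would contribute a 25 mg concentration to the 3 mg summary. A participant randomised to placebo who was given active tablets would show up as drug in placebo CSF.

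Two features of Part B would let such an error carry through to the sample. Section 7.1.2 says the 3 mg, 25 mg and placebo tablets look identical, and it supplies all doses on Days 1 to 7 from one Bottle 1. A wrong bottle would therefore cover the whole Day 2 to 4 sampling window without being visible. What is at stake is the accuracy of a small descriptive table, because each arm-by-timepoint cell may hold few samples.

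**Working it through.** There is no figure in the plan to reproduce: Section 10.1.2 states that Part B is not sized on power, and the point concerns a grouping rule. The arithmetic below only shows how far one misplaced value could move a cell mean.

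**Inputs from the protocol**
- Tablet strengths 3 mg and 25 mg (Section 7.1.2): dose ratio 25/3 = 8.33.
- 40 participants planned per arm (Section 5.1.2), one CSF sample each, alternating predose and postdose (Section 9.5): at most about 40/2 = 20 samples per arm per timepoint if everyone consents. The alternation is within site, not within arm, so 20 is approximate.

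**Assumptions, because the documents give no figure**
- Samples per cell, m: 3 to 20.
- Ratio R of CSF exposure at 25 mg to that at 3 mg: 2 to 8.33. Section 3 says only that CSF exposure rises with dose. R = 8.33 is exact dose proportionality.

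**One 25 mg taker kept in the 3 mg cell.** The arithmetic mean is multiplied by ((m − 1) + R)/m = 1 + (R − 1)/m. The geometric mean is multiplied by R^(1/m).

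| m | Arithmetic, R = 2 | Arithmetic, R = 4 | Arithmetic, R = 8.33 | Geometric, R = 8.33 |
|---|---|---|---|---|
| 3 | 1.33 | 2.00 | 3.44 | 2.03 |
| 5 | 1.20 | 1.60 | 2.47 | 1.53 |
| 10 | 1.10 | 1.30 | 1.73 | 1.24 |
| 20 | 1.05 | 1.15 | 1.37 | 1.11 |

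For example, with m = 3 and R = 8.33: 1 + 7.33/3 = 3.44. With m = 20 and R = 2: 1 + 1/20 = 1.05.

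**One 3 mg taker kept in the 25 mg cell.** The arithmetic mean is multiplied by 1 − (1 − 1/R)/m. At R = 8.33, 1 − 1/R = 0.88, which gives 0.71 (m = 3), 0.82 (m = 5), 0.91 (m = 10) and 0.96 (m = 20). A smaller R brings these closer to 1.

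**One 25 mg taker kept in the placebo cell.** The true placebo concentration is zero, so the placebo mean becomes 1/m of the 25 mg mean: 33%, 20%, 10% and 5% for m = 3, 5, 10 and 20.

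**After the change.** With grouping by treatment received, the value moves to the dose taken, each factor returns to 1.00 and the placebo mean returns to zero. Sample size, power and significance level are unaffected.

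**The case against.** Four arguments stand against giving this much weight.

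*The Part B SAP has not been seen.* Section 10.3 says that a separate Part B SAP will set out the analysis populations in detail, so it could settle the grouping. That is possible, but the sentence in Section 10.2.2 is explicit, and an unseen document cannot be assumed to override it.

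*The triggering event is unlikely.* Sampling falls in the inpatient week. Treatment is assigned centrally by IWRS (Section 7.3), staff give each dose and record its date and time (Section 7.6.2), and dose modification is not allowed (Section 7.2). A missed dose does not put a sample under the wrong label; that takes tablets from the wrong arm before the sample. This argument stands and limits the point. A reader might infer from it that misdosing has happened. The documents report none; Section 9.2.7 only lists the kinds of error that could occur.

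*The size depends on choices the plan has not made.* A reader might infer that one misplaced value would dominate its cell. That holds only for very few samples, near dose-proportional exposure, an arithmetic mean and the 25-into-3 mg direction. Section 10.3.3 does not name the summary statistic; a geometric mean moves less, and a median usually would too.

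*No decision hangs on these data.* A reader might take the CSF samples as meant to establish central exposure at each dose. The documents do not say so. Section 4.2 lists a descriptive CSF analysis among the additional endpoints and ties no efficacy, safety or dose decision to it.

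**Conclusion.** The point holds in conditional form. The randomised-arm rule does not suit a descriptive concentration summary, and it would mislabel a CSF value if a participant took another arm's tablets before sampling. With no misdosing, the effect is zero. With one 25 mg taker in the 3 mg cell, the arithmetic mean is multiplied by about 1.05 to 3.4 over the assumed ranges of exposure ratio and cell size. In the reverse direction, the factor is about 0.71 to 0.96 under dose proportionality.

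The point is minor: the CSF analysis is optional and exploratory, and the MADRS analyses do not use it. It does not extend to the mITT or PD populations. Their grouping by randomised treatment is a separate question, and nothing here shows it to be wrong.

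**What to change.** In Section 10.2.2, change the last sentence of the PK population definition so that participants are grouped by the study treatment actually received before the CSF sample. Add that anyone who took tablets from more than one arm before sampling is listed separately and left out of the dose summaries. Put the same rule in the Part B SAP.

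The cost is a sentence or two. The dosing records in Section 7.6.2 and the drug disposition records already planned should supply the information, and no procedure or participant burden changes. There is one small downside. The PD population would still be grouped as randomised, so a misdosed participant could sit in one group for CSF and another for qEEG/ERP. A footnote to the affected tables would deal with that.

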10.3. Statistical Analyses

There will be 2 separate SAPs, 1 each for Part A and Part B. Each SAP will be developed and finalized before database lock for that part of the protocol and will describe in detail the participant populations to be included in the analyses, the safety and efficacy analysis, and the

procedures for accounting for missing or unscheduled data. This section is a summary of the planned statistical analyses of the primary and secondary endpoints.

10.3.1. Efficacy Analyses (Part A and Part B)

The efficacy analyses will be based on the mITT population of each Part, A or B, respectively. Baseline for efficacy for Part A and Part B, respectively, is defined as the last nonmissing efficacy assessment before the 1st dose of study treatment in each corresponding part of the study. All statistical tests will be 2-sided hypothesis tests performed at the 5% level of significance for main effects. All confidence intervals will be 2-sided 95% confidence intervals, unless stated otherwise.

For efficacy analyses in which study center is a factor, a small center will be defined as a center with fewer than 2 participants for at least 1 treatment group in the mITT Population. All the small centers will be pooled to form a pseudo-center. If the pseudo-center is still a small center, it will be pooled with the smallest non-small center. If there is more than one smallest non-small center, the small pseudo-center will be pooled with the smallest non-small center that has the largest center number.

10.3.1.1. Primary and Secondary Endpoints (Part A and Part B)

10.3.1.1.1. Part A

The primary and secondary efficacy endpoints are listed below and analyses will be defined in the following sections. All analyses for other efficacy endpoints listed below will be defined in more detail in the SAP for Part A.

Primary efficacy endpoint for Part A of the study:

- Change from baseline (Day 1, predose) in MADRS total score at 1 day after the first dose of treatment (Day 2)

Secondary efficacy endpoint for Part A of the study:

- Change from baseline (Day 1, predose) in MADRS total score at Day 8 and Day 9 after single oral dose, on Day 15 after repeated dose, and on Day 22, 7 days after the completion of AGN-241751 dosing

10.3.1.1.2. Part B

The primary and secondary efficacy endpoints are listed below and analyses will be defined in the following sections. All analyses for other efficacy endpoints listed below will be defined in more detail in the SAP for Part B.

Primary efficacy endpoint for Part B of the study:

- Change from baseline in MADRS at 7 days after first dose of treatment

Secondary efficacy endpoint for Part B of the study:

- Change from baseline in MADRS total score at Day 2, Day 11, Day 14, Day 18, and Day 21, 7 days after the completion of AGN-241751 BID dosing

10.3.1.2. Primary Analyses (Part A and Part B)

The primary analysis for the primary and secondary endpoints in Part A and Part B will be performed using an MMRM with treatment group, visit, pooled study center, and treatment group-by-visit interaction as fixed effects and the baseline value and baseline value-by-visit as covariates. An unstructured covariance matrix will be used to model the covariance of within-participant scores. If the model fails to converge based on the unstructured covariance matrix, then structures of Heterogenous Toeplitz, Toeplitz, and Compound Symmetry will be applied, in the specified order, until the model converges. The Kenward-Roger approximation will be used to estimate denominator degrees of freedom ([Kenward and Roger 1997](#)). These analyses will be performed based on all postbaseline scores using only the OCs without imputation of missing values.

In addition, a sensitivity analysis using the MI approach under MNAR assumptions will be performed on the primary and secondary efficacy parameters.

Detailed methods and procedures for the above outlined missing data-derived sensitivity analyses will be documented in the final SAPs prior to the study database locks.

10.3.1.3. Additional Efficacy Parameters (Part A and Part B)

10.3.1.3.1. Part A

Additional efficacy parameters are as follows, with the Day 1 (predose) value serving as the baseline:

- Change from baseline in CGI-S total score at Day 2, Day 8, Day 9, and Day 15
- Rate of responders on MADRS or CGI-S at Day 2, Day 8, Day 9, Day 15, and Day 22
- Rate of remitters on MADRS at Day 2, Day 8, Day 9, Day 15, and Day 22
- Time to first response on MADRS
- Time to first remission on MADRS

Analysis of change from baseline in MADRS total score and CGI-S score will be performed using a similar MMRM to that used for the key secondary parameter.

CGI-S responder is defined as participants achieving a score of ≤ 2 on the CGIS of Illness scale.

CGI-S sustained responder: Meet responder criteria at ≥ 2 consecutive visits and continued through to final assessment.

During the randomized treatment period, 4 types of events for MADRS total score will be defined based on the following criteria:

- Responder: $\geq 50\%$ reduction from baseline MADRS total score
- Sustained responder: Meet responder criteria at ≥ 2 consecutive visits and continued through to final assessment
- Remitter: MADRS total score ≤ 10
- Sustained remitter: Meet remitter criteria at ≥ 2 consecutive visits and continued through to final assessment

Rates of responders and remitters will be reported by treatment group for each timepoint of assessment (Day 1 [predose] defined as baseline and Days 2, 8, 9, 15, and 22 after first dose of randomized treatment). A logistic regression model will be used to model the probability of a response or the probability of a remission as a function of a treatment group, and baseline MADRS or CGI-S total score.

The time to onset of first event is defined as the number of days from the first randomized dosing to the first event. The time to onset in days will be calculated for each type of event (response or remission) in person level. Participants who do not meet the criteria for respective type of event will be censored at the time of their last MADRS assessment during the treatment period.

For each type of event, the proportion of participants with onset of first events, Kaplan-Meier estimate in terms of the median time to onset of first event, and its 95% CI will be presented for each treatment group. Plots of the Kaplan-Meier estimate of the distribution of the time to onset of events will also be provided for each treatment arm. Log-rank tests comparing the time to onset of event distribution between each AGN-241751 dose and placebo will be conducted.

10.3.1.3.2. Part B

Additional efficacy parameters are as follows, with the Day -1 (predose) value serving as the baseline:

- Change from baseline in CGI-S total score by visit
- Rate of responders on MADRS at Day 2, Day 7, Day 11, Day 14, Day 18, and Day 21
- Rate of responders on CGI-S by visit
- Rate of remitters on MADRS at Day 2, Day 7, Day 11, Day 14, Day 18, and Day 21
- Time to first response on MADRS
- Time to first remission on MADRS

Analysis of change from baseline in MADRS total score and CGI-S score will be performed using a similar MMRM to that used for the key secondary parameter.

During the randomized treatment period, 2 types of events will be defined based on the following criteria:

- Responder: $\geq 50\%$ reduction from baseline MADRS total score
- Remitter: MADRS total score ≤ 10

Rates of responders and remitters will be reported by treatment group for each timepoint of assessment (Day -1 [predose] defined as baseline and Days 2, 7, 11, 14, 18, and 21 after the 1st dose of randomized treatment). A logistic regression model will be used to model the probability of a response or the probability of a remission as a function of a treatment group, and baseline MADRS or CGI-S total score.

The time to onset of first event is defined as the number of days from the first randomized dosing to the first event. The time to onset in days will be calculated for each type of event (response or remission) in person level. Participants who do not meet the criteria for respective type of event will be censored at the time of their last MADRS assessment during the treatment period.

For each type of event, the proportion of participants with onset of first events, Kaplan-Meier estimate in terms of the median time to onset of first event, and its 95% CI will be presented for each treatment group. Plots of the Kaplan-Meier estimate of the distribution of the time to onset of events will also be provided for each treatment arm. Log-rank tests comparing the time to onset of event distribution between each AGN-241751 dose and placebo will be conducted.

10.3.2. Exploratory Analyses

10.3.2.1. Part A

The exploratory analyses of HAM-A scores will be performed using the safety population for the double-blind treatment period and for the safety follow-up period, if applicable, and will be fully defined in the SAP. The exploratory parameters will include change from baseline in HAM-A scores Day 2, Day 8, and Day 15. At Visit 2, the HAM-A will be administered with a look-back timeframe of 1 week. At all other evaluations, the HAM-A will be administered with a look-back timeframe of “since last evaluation.” The HAM-A will be collected only from participants entering the study after the amendment has been IRB approved.

10.3.2.2. Part B

The exploratory analyses include the following:

- Analysis of Likert Patient Depressive Symptom Scales of each assessed domains (including depression, anxiety, and sleep quality, etc.) will be performed based on the safety population for the double-blind treatment period and for the safety follow-up period, if applicable, and will be described descriptively and in more detail in the SAP for Part B.
- Analysis of HVLT-R assessment will be performed using the safety population for the double-blind treatment period and for the safety follow-up period, if applicable, and will be described in more detail in the SAP for Part B.

10.3.3. Pharmacokinetic Analysis (Part B Only)

Analysis of the CSF concentrations of AGN-241751 will be performed using the PK population for the double-blind treatment period. Descriptive analysis of the CSF concentrations will be performed.

